## 6.4 Laboratory parameters – direction of interest and definition of clinically notable values

The following table shows the direction of interest when analyzing worst case values in form of maximum and/or minimum post-baseline values. If the direction of interest is given as "High" the maximum value will be calculated and used as worst value, if the direction is given as "Low" the minimum value will be taken, and if it is given as "Low and high", both the minimum value and the maximum value will be calculated and presented in summary tables.

### Direction of interest for worst case value for laboratory parameters

Laboratory Parameter	Direction of interest for worst case value
A. Hematology	
Hemoglobin	Low
Hematocrit	Low
Erythrocytes	Low
WBC	Low and high
Basophils	High
Eosinophils	High
Lymphocytes	Low and high
Monocytes	High
Neutrophils	Low and high
Platelets	Low and high
B. Chemistry	
Albumin	Low
Alkaline Phosphatase	High
ALT/SGPT	High
AST/SGOT	High
Bilirubin Total	High
Blood Urea Nitrogen (BUN)	High
Creatinine	High
Glucose	Low and high
Gamma GT	High
Potassium	Low and high
Magnesium	Low and high
Uric acid	High
Plasma cortisol	Low and high

The following table shows the criteria for clinically notable laboratory values. Not all parameters have notable criteria defined.

Laboratory parameter (unit)	Lower bound of clinically notable range	Upper bound of clinically notable range
Hematology		
Hematocrit (v/v)		
Male	0.37	
Female	0.32	
Hemoglobin (g/L)		
Male	115	
Female	95	
Platelets (x10  /L)	75	700
WBC (x10  /L)	2.8	16.0
Chemistry		
Albumin (g/L)	25	-
Alkaline Phosphatase (U/L)	-	3xULN
ALT/SGPT (U/L)	-	3xULN
AST/SGOT (U/L)	-	3xULN
Bilirubin Total (mcmol/L)	-	34.2
BUN (mmol/L)	-	9.99
Creatinine (mcmol/L)	-	176.8
Glucose (mmol/L)	2.78	9.99
Gamma GT (U/L)	-	3 x ULN
Potassium (mmol/L)	3	6
Magnesium (mmol/L)	0.51	1.07

v = volume, ULN = upper limit of normal

**Notable liver function test values**

Criterion
ALT > 3 x the upper limit of normal range (ULN) ALT > 5 x ULN ALT > 8 x ULN ALT > 10 x ULN ALT > 20 x ULN
ALT or AST > 3 x ULN ALT or AST > 5 x ULN ALT or AST > 8 x ULN ALT or AST > 10 x ULN ALT or AST > 20 x ULN
Total bilirubin > 1 x ULN Total bilirubin > 1.5 x ULN Total bilirubin > 2 x ULN Total bilirubin > 3 x ULN
ALP > 1.5 x ULN ALP > 2 x ULN ALP > 3 x ULN ALP > 5 x ULN
ALT or AST > 3 x ULN and total bilirubin > 1.5 x ULN ALT or AST > 3 x ULN and total bilirubin > 2 x ULN ALT or AST > 5 x ULN and total bilirubin > 2 x ULN ALT or AST > 8 x ULN and total bilirubin > 2 x ULN ALT or AST > 10 x ULN and total bilirubin > 2 x ULN ALT or AST > 20 x ULN and total bilirubin > 2 x ULN
ALP > 3 x ULN and total bilirubin > 2 x ULN ALP > 5 x ULN and total bilirubin > 2 x ULN
ALT or AST > 3 x ULN and Total Bilirubin > 2 x ULN and ALP < 2 x ULN (Hy's law)
ALT or AST > 3 x ULN and (nausea or vomiting or fatigue or general malaise or abdominal pain or (rash and eosinophilia))*

ALT = alanine aminotransferase, AST = aspartate aminotransferase, ALP = alkaline phosphatase

\* Based on the signs/symptoms information as recorded on the liver events eCRF, not the adverse events eCRF.

## 6.5 Vital signs and ECG – definition of clinically notable values

The following table shows the clinical notable criteria for vital signs.

Vital sign parameter (unit)	Lower bound of clinically notable range	Upper bound of clinically notable range
Notable value considering newly occurring or worsening cases		
Systolic blood pressure (mmHg)	< 75	> 200
Diastolic blood pressure (mmHg)	< 40	> 115
Pulse rate (bpm)	< 40	> 130
Notable change from baseline		
Systolic blood pressure (mmHg)	≤ 90 and decrease from baseline by ≥ 20	≥ 180 and increase from baseline by ≥ 20
Diastolic blood pressure (mmHg)	≤ 50 and decrease from baseline by ≥ 15	≥ 105 and increase from baseline by ≥ 15
Pulse rate (bpm)	≤ 50 and decrease from baseline by ≥ 15	≥ 120 and increase from baseline by ≥ 15

The following table shows the clinical notable criteria for QTcF.

**Clinical notable criteria for QTcF (Fridericia's formula)**

ECG parameter (unit)	Clinically notable range
Notable value considering newly occurring or worsening cases	
QTc (msec)	> 450 (male)
QTc (msec)	> 460 (female)
QTc (msec)	> 500 (both)
Notable change from baseline	
QTc	30 – 60
QTc	> 60
Combined criterion QTc (msec)	> 500 & increase from baseline > 60

## 6.6 Statistical methodology and assumptions

SAS codes for all statistical methodology described in this section will be included as programming note in TFL Shells.

- **Mixed Model Repeated Measures (MMRM)**

The following MMRM ANCOVA will be used for trough FEV1, ACQ-7, and other data:

Dependent variable = intercept + treatment + age group + region + baseline value + FEV1 prior to inhalation + FEV1 within 15 to 30 min post inhalation + visit + treatment\*visit + baseline value\*visit + random effect of center nested within region + error.

The within-patient correlation will be modeled using an unstructured covariance matrix in the mixed model. The Kenward-Roger approximation will be used to estimate denominator degrees of freedom (Kenward and Roger, 1997).

For the final analysis, if the model does not converge with unstructured covariance matrix, the compound symmetry covariance structure will be used, if the model still does not converge the random effect will be removed, if the model converges after removing the random center effects, the original model without random center effects will be re-assessed

The SAS procedure PROC MIXED will be used for analysis. Results will be presented with least squares mean (LSM) and standard error (SE) for treatment effects and LSM, SE, associated two-sided 95% confidence interval, and two-sided p-value for the treatment contrast.

In the analysis of laboratory data [REDACTED], the covariates FEV1 prior to inhalation and FEV1 15 to 30 min post inhalation will not be included in the MMRM.

- **Tipping point analysis for trough FEV1 at Week 12**

As a sensitivity analysis to evaluate the impact of missing data, a tipping point analysis will be performed for the primary endpoint trough FEV1 at Week 12. The delta-adjusting approach described in Ratitch et al (2013) will be used to find the tipping point, in a spectrum of conservative missing not at random (MNAR) assumptions, at which conclusions change from being favorable to QMF149 to being unfavorable. The basic idea is to impute the missing values using a regression based multiple imputation (MI) method based on the MAR assumption. The imputed Week 12 values for the QMF149 arms are then adjusted by a delta value.

The endpoint is assumed to have a normal distribution at Day 2 and Week 12. The primary analysis is performed on the delta-adjusted datasets to see if the conclusions change. If not, a larger delta is chosen and the process is repeated until the conclusion is overturned. The tipping point is the delta value which will cause the QMF149 vs. MF comparison on the primary endpoint to be no longer statistically significant. A series of analyses on a range of delta values will be performed to find the tipping point. For each delta value, the following steps will be performed.

1. Impute missing covariates (baseline FEV1, FEV1 prior to inhalation and FEV1 15 to 30 min post inhalation value) and missing values at Day 2 and/or Week 12 using the MI approach based on the fully conditional specification (FCS) method for 100 times and obtain 100 imputed datasets. Missing baseline FEV1, FEV1 prior to inhalation and FEV1 15 to 30 min post inhalation value will be imputed separately for each treatment group using a model with age group, geographic region, and the respective other covariates (baseline FEV1, FEV1 prior to inhalation and FEV1 15 to 30 min post inhalation value) as predictors. Missing Day 2 values will be imputed separately for each treatment group using a model with the imputed values of age group, geographic region, baseline FEV1, FEV1 prior to inhalation and FEV1 15 to 30 min post inhalation value as predictors. Missing Week 12 values will be imputed separately for each treatment group using a model with the imputed values of age group, geographic region, baseline FEV1, FEV1 prior to inhalation, FEV1 15 to 30 min post inhalation, and Day 2 value as predictors.
2. After the imputation obtained in above step, for subjects in the QMF149 treatment arms only, make the imputed value at Week 12 worse by a value of delta (i.e., subtract delta from the imputed value at Week 12). Note: delta = 0 represents the standard missing at random (MAR) based MI.
3. The final multiply-imputed dataset where all missing values are filled will be analyzed (by imputed dataset) using a linear mixed model with treatment, age group, geographic region, baseline FEV1, FEV1 prior to inhalation, and FEV1 within 15 to 30 min post inhalation as predictors.
4. The results for the treatment effect from the 100 datasets will then be combined using Rubin's rule. If the combined results does not change the conclusion (i.e., the QMF149 treatment effect is still statistically significantly superior to MF), a larger delta will be chosen and Steps 1-4 will be repeated using the datasets from Step 2 until the tipping point is found (when  $p > 0.05$ ).

- **Logistic regression analysis**

The analysis of proportion of patients who achieve an improvement of at least 0.5 in ACQ-7 (i.e. decrease of ACQ-7 score of at least 0.5 from Baseline) at post-baseline visits will be performed using the following steps:

1. Impute missing covariates (baseline ACQ-7, FEV1 prior to inhalation and FEV1 15 to 30 min post inhalation value) and missing continuous ACQ-7 values at Day 30 and/or Week 12 using the MI approach based on the fully conditional specification (FCS) method for 100 times and obtain 100 imputed datasets. Missing baseline ACQ-7, FEV1 prior to inhalation and FEV1 15 to 30 min post inhalation value will be imputed separately for each treatment group using a model with age group, geographic region, and the respective other covariates (baseline ACQ-7, FEV1 prior to inhalation and FEV1 15 to 30 min post inhalation value) as predictors. Missing Day 30 values will be imputed separately for each treatment group using a model with the imputed values of age group, geographic region, baseline ACQ-7, FEV1 prior to inhalation and FEV1 15 to 30 min

post inhalation value as predictors. Missing Week 12 values will be imputed separately for each treatment group using a model with the imputed values of age group, geographic region, baseline FEV1, FEV1 prior to inhalation, FEV1 15 to 30 min post inhalation, and Day 30 value as predictors.

The SAS procedure PROC MI will be used and this will result in 100 copies of the original dataset.

2. Then continuous ACQ values will be converted into binomial responses (1= an improvement of at least 0.5, 0= no improvement) and generalized estimating equation (GEE) method will be used to analyze the dataset. The GEE model will include terms for treatment, age (12 to 17 or  $\geq 18$  years), region, visit, and treatment-by-visit interaction as fixed effects, and Baseline ACQ-7, Baseline-by-visit interaction, FEV1 prior to inhalation and FEV1 within 15 to 30 min post inhalation of salbutamol/albuterol (components of SABA reversibility) as covariates.

The SAS procedure PROC GENMOD will be used.

Combining results from X copies of original dataset:

3. In the next step, results from each copy, obtained from GEE method will be combined for the inference using Rubin's rule. The SAS procedure PROC MIANALYZE will be used for combining the results considering the linear scale and then we will take exponential of combined result to obtain the odds ratio.

The estimated adjusted odds ratio will be displayed along with the associated 95% confidence interval and p-value (two-sided).

The proportion of patients who achieve an improvement of at least 0.5 at Week 12 in the change from baseline in AQLQ (i.e. increase of AQLQ score of at least 0.5 from baseline) will be analyzed using the same procedure as mentioned above for ACQ-7, with the following changes:

Replace ACQ-7 in all steps by AQLQ. Change step 1 as follows.

1. In Step 1, Impute missing covariates (baseline AQLQ, FEV1 prior to inhalation and FEV1 15 to 30 min post inhalation value) and missing continuous AQLQ values at Week 12 using the MI approach based on the fully conditional specification (FCS) method for 100 times and obtain 100 imputed datasets. Missing baseline AQLQ, FEV1 prior to inhalation and FEV1 15 to 30 min post inhalation value will be imputed separately for each treatment group using a model with age group, geographic region, and the respective other covariates (baseline AQLQ, FEV1 prior to inhalation and FEV1 15 to 30 min post inhalation value) as predictors. Missing Week 12 values will be imputed separately for each treatment group using a model with the imputed values of age group, geographic region, baseline AQLQ, FEV1 prior to inhalation, FEV1 15 to 30 min post inhalation.

- **Linear Mixed Model Analysis of Covariance (ANCOVA)**

The following linear mixed ANCOVA model will be used for diary data summarized over 12 weeks:

Dependent variable = intercept + treatment + age group + region + baseline value + FEV1 prior to inhalation + FEV1 within 15 to 30 min post inhalation + random effect of center nested within region + error.

The SAS procedure PROC MIXED will be used for analysis. Results will be presented with LSM and SE for treatment effects and LSM, SE, associated two-sided 95% confidence interval, and two-sided p-value for the treatment contrast.

- **Cox regression analysis**

A Cox proportional hazards regression model stratified by age (12 to 17,  $\geq 18$  years) will be applied in time-to-event analyses to test the null-hypothesis  $H_0: \lambda_{\text{QMF}}(t) / \lambda_{\text{Control}}(t) = 1$ , where  $\lambda(t)$  is the hazard function for the failure time of patients treated with QMF and the control group, respectively.

The SAS procedure PHREG will be used for analysis. Results will be presented with adjusted hazard ratio for the treatment group comparison and associated 95% confidence interval and two-sided p-value. P-value will be obtained from the Wald chi-squared statistic testing the null-hypothesis that the parameter estimate for the respective treatment effect is 0 (then the hazard ratio is  $\exp(0) = 1$ ).

No check for the validity of proportional hazards assumptions will be done.

- **Generalized linear model assuming a negative binomial distribution**

The annual rate of asthma exacerbations (by exacerbation category) will be analyzed using a generalized linear model assuming a negative binomial distribution.

The time at risk for a patient is defined as the duration of exposure in days + 1 day and the  $\log(\text{time at risk in years})$  will be used as the offset variable in the model.

The SAS procedure GENMOD will be used for analysis. Treatment group ratio of exacerbation rate will be presented together with 95% confidence interval and two-sided p-value.

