#### **2.5.4 Supportive and Sensitivity analyses**

As supportive analysis, the same MMRM used in the primary analysis will be also performed on the PPS to assess the treatment effect in protocol adherers.

In addition, the same primary MMRM on the FAS will be performed including all spirometric measures irrespective of systemic corticosteroid or rescue medication use but those measures taken outside of the 22 – 25 hour post-evening dose time window will not be included.

As a sensitivity analysis, a so-called 'tipping point analysis' will be performed for the primary endpoint to evaluate the impact of a deviation from the MAR assumption of missing data. The delta-adjusting approach described in Ratitch et al (2013) will be used to find the tipping point, in a spectrum of conservative missing not at random (MNAR) assumptions, at which conclusions change from being favorable to QMF149 to being unfavorable. After such a tipping point is determined, clinical judgment can be applied as to the plausibility of the assumptions underlying this tipping point. This methodology would provide a good picture of what it would take to overturn study conclusions on the basis of varying assumptions about missing data. The basic idea is to first impute the missing values using a regression based multiple imputation (MI) method based on the MAR assumption. The imputed Week 12 values for the QMF149 arms are then adjusted by a delta value. A detailed description of the analysis steps are provided in [Section 6.6](#).

The exploratory subgroup analyses for trough FEV1 using MMRM will be performed (using the appropriate interaction term in the model and additional covariate as a fixed effect, if necessary) for the FAS population to explore the treatment effect in key demographic and disease related subgroups (See [Section 2.2.1](#) for the details of subgroups).

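### SAP 6.6, Step 4 of the tipping-point analysis: the instruction to reuse the Step 2 datasets, read literally, adds successive deltas together and would mislabel the tipping point

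*SAP*

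**What the plan says.** SAP 2.5.4 and 6.6 plan a delta-adjusted sensitivity analysis for the primary endpoint. Missing values are imputed under MAR, and then: "The imputed Week 12 values for the QMF149 arms are then adjusted by a delta value".

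SAP 6.6 introduces the numbered procedure with "For each delta value, the following steps will be performed". The steps are:

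- **Step 1:** impute missing covariates, Day 2 and Week 12 values, giving 100 datasets.
- **Step 2:** in the QMF149 arm only, "subtract delta from the imputed value at Week 12". It adds: "Note: delta = 0 represents the standard missing at random (MAR) based MI".
- **Step 3:** analyse the result, described as "The final multiply-imputed dataset where all missing values are filled".
- **Step 4:** combine by Rubin's rule. If QMF149 is still significantly superior, "a larger delta will be chosen and Steps 1-4 will be repeated using the datasets from Step 2 until the tipping point is found".

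The tipping point is defined as the delta at which significance is lost. SAP 2.5.4 states its use: "clinical judgment can be applied as to the plausibility of the assumptions underlying this tipping point". SAP 6.6 also says that SAS code for these methods will be included in the TFL shells.

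**The concern.** Step 4 names as input a set of data that Step 2 has already altered. Taken at its word, this causes two problems. The new, larger delta is subtracted from QMF149 values that already contain the old one. And Step 1, which the same sentence orders repeated, has no missing values left to fill.

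The tipping delta is the result of this analysis, and a reader is invited to judge its clinical plausibility. If the labelled delta is not the shift from MAR that was applied, that judgment is made on the wrong number.

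**Working it through.** **Comparing the texts.**

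| Place in SAP | What it implies for the next delta |
|---|---|
| 6.6, lead-in to the steps | All steps, including MAR imputation, are run for each delta |
| 6.6, Step 2 | Delta is one subtraction from the imputed value; zero is the MAR analysis |
| 6.6, Step 4 | The repeat uses the Step 2 datasets, which are shifted and complete |
| 2.5.4 and 6.6 overview | Consistent with a single shift of MAR-imputed values; silent on how the search iterates |

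The conflict is therefore inside SAP 6.6, between Step 4 and the lead-in with Step 2.

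**Inputs.** From SAP section 3: effect 100 mL, SD 380 mL, 375 per arm, 10% dropout. These reproduce the plan's power. With 338 per arm, primary power is 92.8% (stated: about 93%). ACQ-7 power is 83.3%, and 0.928 × 0.833 = 77.3% (stated: 77%). The SAP gives no tipping point, delta grid or expected missingness pattern. Assumed here: the observed effect equals 100 mL, a fraction f = 10% of Week 12 values is missing in each arm, and delta rises in steps of 50 mL.

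**Shift at which significance is lost.** A shift d of the imputed QMF149 values lowers the estimate by f × d and adds some variance within that arm. The limit solves

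E − f·d = 1.96 × √[ 2·380² / (375(1 − f)) + f(1 − f)·d² / 375 ].

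With E = 100 and f = 0.10, d = 413.1 mL. Check: the left side is 100 − 41.31 = 58.69. The right side is 1.96 × √(855.70 + 40.96) = 58.69.

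**Correct search, each delta taken from MAR.**
- At 400 mL: 60.0 against 58.6, still significant.
- At 450 mL: 55.0 against 58.9, not significant. Reported delta: 450 mL.

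**Literal Step 4, deltas added.** Nominal deltas of 50, 100, 150 and 200 mL give applied shifts of 50, 150, 300 and 500 mL.
- At nominal 150 (applied 300): 70.0 against 58.1, still significant.
- At nominal 200 (applied 500): 50.0 against 59.3, not significant. Reported delta: 200 mL.

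The label is 450 / 200 = 2.25 times too small. If the accumulated shift is reported instead, it is 500 mL, against 450 mL from a correct search.

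**Cross-checks.** The simpler form (100 − 1.96 × 380 × √(2/338)) / 0.10 gives 427 mL and the same two labels. Simulation with 100 imputations and Rubin's rule (15 trials, assumed Day 2 correlation 0.5) gave median labels of 450 and 200 mL. A single simplified run gave 400 and 200 mL, with 500 mL applied in the second case. In that run a true 200 mL shift was still significant (p = 0.009).

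**Sensitivity to the assumptions.** Over effects of 80 to 120 mL (the SAP's quoted range), 5 to 15% missing and steps of 10 to 100 mL, the ratio of correct to compounded label runs from 1.0 to 7.9. The low end is 80 mL, 15% missing and 100 mL steps: both searches report 200 mL. The high end is 120 mL, 5% missing and 10 mL steps: 1180 / 150.

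**The case against.** The best defence is that Step 4 only restates the paragraph above the steps. That paragraph says the delta-adjusted data are analysed and, if the conclusion stands, a larger delta is chosen and the process repeated. On this view the Step 2 datasets are simply each pass's own new output, feeding Step 3. Because Steps 1 to 4 are all repeated, every pass imputes afresh and nothing accumulates. A second harmless reading is that the phrase points to a first pass at delta zero, whose Step 2 data are unshifted. Both are reasonable guesses at the intent, and the literal reading's empty Step 1 argues for them. But the SAP states neither, and it does not say that the search starts at zero.

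This defence does rule out some stronger conclusions that a reader might draw:

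- **That Step 4 cannot be reconciled with the rest, or that nothing in the SAP removes the earlier shift.** Rerunning Step 1 for each delta, as the lead-in requires, restores unshifted values. The phrase is ambiguous; it does not make the method unworkable.
- **That SAP 2.5.4 prescribes a different search.** It describes the adjustment but not the iteration.
- **That the error is always conservative.** It makes QMF149 look more fragile only if the last nominal delta is reported. If the accumulated shift is reported, the figure overshoots and QMF149 looks somewhat sturdier than it is.
- **That the size is known.** It depends on a grid and a missingness pattern that the SAP does not give.

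The programmed version may also be right. The TFL shells are not among the documents, so this could not be checked.

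**Conclusion.** The point stands as a minor wording error in SAP 6.6, probably a drafting slip. The mislabelling arises only if the phrase is followed literally in the code. The 450 against 200 mL example shows the kind of discrepancy possible under the assumptions above; it is not a forecast for this trial.

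The reach is this one sensitivity analysis. A reader might infer that the primary result is in doubt, but the documents do not support that: the primary MMRM, its test, type I error and power do not use the tipping-point datasets. If the SAS code already subtracts each delta from unshifted MAR-imputed values, only the text is wrong.

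**What to change.** The simplest change is to delete from Step 4 the words that direct the repeat to the Step 2 datasets. The sentence then agrees with the lead-in, under which every step is run for each delta.

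Alternatively, state that Step 1 is run once and that Steps 2 to 4 are repeated for each delta, always subtracting the new delta from the unshifted MAR-imputed Step 1 datasets. The lead-in must then be changed to match.

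In either case, confirm that the SAS code in the TFL shells follows the same rule. The cost is one phrase, or one sentence plus the lead-in, and a code check. No new data or analysis is needed, and the primary analysis does not change.

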## 2.6 Analysis of the key secondary objective

### 2.6.1 Key secondary endpoint

The key secondary objective is to demonstrate the superiority of QMF149 150/80 µg to MF 200 µg in terms of ACQ-7 after 12 weeks of treatment.

The ACQ-7 measures asthma symptom control and consists of seven items: five on symptom assessment, one on rescue bronchodilator use and one on airway calibre (FEV1 % predicted). Patient recall is one week. All 7 questions of the ACQ-7 are equally weighted. Items 1-5 are scored along a 7-point response scale, where 0 = good controlled and 6 = poor controlled. Item 6 is scored between 0 = no rescue medication and 6 = More than 16 puffs/inhalations most days. The 7th item will be scored by the investigator based on the FEV1 % predicted from the masterscope at the site (i.e., Score = 0 means > 95% of predicted FEV1, 1 = 90 – 95%, 2 = 80 – 89%, 3 = 70 – 79%, 4 = 60 – 69%, 5 = 50 – 59%, and Score = 6 means < 50% of predicted FEV1). The total score is calculated as the mean of all questions. The mean will be calculated as the sum of scores divided by the number of questions that were answered, as long as there were at least 6 questions answered and the missing question is neither Question 1 ('On average, during the past week, how often were you woken by your asthma during the night?') nor Question 7. In case of one missing response (not Question 1 or Question 7), first that missing response will be imputed as per the method given in [Section 2.6.3](#) and then the ACQ score will be calculated.

ACQ-7 measurements are scheduled for Days -21, 1, 30 and 84.

For the ACQ-7 score, the baseline value is defined as the score obtained at Day 1 prior to first dose of study treatment. If the value is missing, the last measurements from run-in visit 101 or unscheduled run-in visits will be used.

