## **2.7.2 Asthma control questionnaire (ACQ)**

Results for ACQ-7 at day 30, obtained from MMRM for the key secondary endpoint ACQ-7 at day 84, will be displayed.

Change from baseline in the ACQ-7 will be also analyzed using the same MMRM model.

The proportion of patients who achieve an improvement of at least 0.5 in ACQ-7 (i.e. decrease of ACQ-7 score of at least 0.5 from Baseline) at post-baseline visits will be analyzed using a logistic regression model. First missing ACQ-7 values will be imputed using a regression based Multiple Imputation (MI) method under missing at random (MAR) assumption, based on continuous ACQ values. Then continuous ACQ values will be converted into binomial responses and generalized estimating equation (GEE) method will be used to analyze the datasets and then the results from GEE method will be combined for the inference. The GEE model will include terms for treatment, age (12 to 17 or  $\geq 18$  years), region, visit, and treatment-by-visit interaction as fixed effects, and Baseline ACQ-7, Baseline-by-visit interaction, FEV1 prior to inhalation and FEV1 within 15 to 30 min post inhalation of salbutamol/albuterol (components of SABA reversibility) as covariates. The estimated adjusted odds ratio will be displayed along with the associated 95% (2 -sided) confidence interval and p-value.

Additionally, the number of patients will be summarized by response relative to baseline ACQ-7 with the following categories: Response (decrease of  $\geq 0.5$  units in ACQ-7), No change ( $-0.5 < \text{change in ACQ-7} < 0.5$ ), Worsening (increase of  $\geq 0.5$  units in ACQ-7), Net response (response – worsening) and Total.

In addition to ACQ-7, average of first 5 questions in ACQ (ACQ-5) will be calculated and all the analyses described for ACQ-7 will be repeated for ACQ-5.

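### The imputation models for the earlier visit leave out Week 12, so an imputed Day 30 ACQ-7 (or Day 2 trough FEV1) carries no link to an observed Week 12 value; the effect is small and the repair is free

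*SAP*

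**What the plan says.** SAP 2.7.2 analyses the proportion of patients improving by at least 0.5 in ACQ-7 at the post-baseline visits. Missing scores are first filled in by a "regression based Multiple Imputation (MI) method under missing at random (MAR) assumption, based on continuous ACQ values". There are two such visits: "ACQ-7 measurements are scheduled for Days -21, 1, 30 and 84", the last two being post-baseline.

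SAP 6.6, under the logistic regression heading, gives the detail in Step 1. It covers "missing continuous ACQ-7 values at Day 30 and/or Week 12", so gaps at Day 30 alone are in scope, and it works "using the MI approach based on the fully conditional specification (FCS) method for 100 times and obtain 100 imputed datasets". It then lists predictors visit by visit:

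- **Day 30:** "Missing Day 30 values will be imputed separately for each treatment group using a model with the imputed values of age group, geographic region", plus baseline ACQ-7 and FEV1 before and after the reversibility bronchodilator. The list stops there: "post inhalation value as predictors. Missing Week 12 values will be imputed separately for each treatment group".
- **Week 12:** the list ends "post inhalation, and Day 30 value as predictors".

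Conditioning therefore runs from Day 30 to Week 12 and not back.

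Step 1 of the tipping-point analysis in the same section is built the same way for trough FEV1. Its Day 2 rule is "Missing Day 2 values will be imputed separately for each treatment group using a model with the imputed values of age group, geographic region", plus baseline and reversibility FEV1, without Week 12. Its Week 12 model includes Day 2. No other section of the SAP gives a different predictor list.

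**The concern.** Fully conditional specification is chosen when gaps need not be monotone, and it ordinarily predicts each incomplete variable from all the others. The SAP names that method but writes out a one-way list that suits monotone dropout. A programmer following the method's name and one following the list could produce different datasets.

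Under MAR, missingness may depend on anything observed, including a later score. An imputation that leaves out the observed Week 12 score is valid only under a narrower assumption. The SAP elsewhere treats the later visit as informative: for a single missing ACQ item, SAP 2.6.3 borrows from the following visit first, and the ACQ-7 MMRM, with its unstructured covariance, lets Week 12 inform Day 30.

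Two things are at stake: the slope used to impute Week 12, and the Day 30 responder proportions.

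**Working it through.** The SAP states no figure that tests this, so the check is on how the written scheme behaves.

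**Inputs from the documents.** 375 patients per arm, ACQ-7 SD 0.80, treatment difference -0.18 and 10% dropout (SAP 3).

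**Assumed, because the documents are silent.** The Day 30 to Week 12 residual correlation, the share of patients with Day 30 missing and Week 12 observed, the missingness mechanism, and a true Day 30 responder rate of about 55%.

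**1. Slope dilution, random gaps.** Among patients with Week 12 observed, let f be the share whose Day 30 value is imputed without Week 12. Those rows have about the right variance but no residual covariance with Week 12. Hence

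fitted slope ≈ true slope × (1 − f)

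- f = 3%: 0.65 × 0.97 = 0.63
- f = 6%: 0.65 × 0.94 = 0.61

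Simulation gives the same 0.63 and 0.61. The responder rate stays unbiased (0.550 against a true 0.550). Adding Week 12 returns the slope to 0.65.

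**2. Day 30 rate, gaps dependent on observed Week 12.** Take missingness with a logistic slope of 1 per SD of Week 12 score, worse control being more often missing. In simulation, the true Day 30 responder rate among those missing is then about 31% (3% gaps) or 32% (6% gaps). The written model fills them at the rate of those observed:

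observed rate = (0.55 − f × rate in missing) / (1 − f)

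- f = 3%: (0.55 − 0.03 × 0.31) / 0.97 = 0.557, an excess of 0.7 points
- f = 6%: (0.55 − 0.06 × 0.32) / 0.94 = 0.565, an excess of about 1.4 to 1.5 points (simulation 1.4)

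The slope falls to 0.62 and about 0.59. Adding Week 12 restores both the rate (0.550) and the slope (0.65).

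**3. Gaps dependent on the unobserved Day 30 score (outside MAR).** The written scheme overstates the rate by 1.1 points at 3% and 2.1 at 6%. With Week 12 added, 0.6 and 1.2 points remain.

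**4. Treatment comparison.** A two-arm simulation used 375 per arm, 10% Week 12 dropout, correlations of 0.5 and 0.8, and nominal Day 30 gaps of 2%, 5% and 10% (100 replicates, 3 imputations each).

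| Quantity | As written | With Week 12 added |
|---|---|---|
| Residual correlation in rows with imputed Day 30 (true 0.5 / 0.8) | −0.01 to 0.04 | 0.46–0.49 / 0.76–0.79 |
| Excess Day 30 rate, gaps dependent on Week 12 | 0.5 to 3.8 points, both arms | 0.2 points or less |
| Day 30 log odds ratio, worst case (correlation 0.8, 10% gaps) | bias 0.014 | bias 0.004 |
| Week 12 log odds ratio | within noise (about 0.01) | within noise |

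For scale, at 375 per arm and 55% the standard error of a log odds ratio is √(2 / (375 × 0.55 × 0.45)) = 0.147. The worst bias of 0.014 is under a tenth of that. One arm's proportion has a standard error of √(0.55 × 0.45 / 375) = 2.6 points, so 0.7 points is about a quarter of it.

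**The case against.** The strongest reply is that nothing reported as a treatment comparison changes. The output promised from this analysis is an adjusted odds ratio. Any excess in the Day 30 rate arises in both arms and nearly cancels. The listed secondary objective is response at Week 12 (Protocol 2.3, SAP 1.2.3). This stands, and it is why the point is minor.

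The affected pattern may also be rare. Off-treatment efficacy data are not used (Protocol 9), discontinuation-visit data do not feed imputation unless otherwise specified (SAP 6.3), and contacts after discontinuation are by telephone without ACQ-7 (Protocol Table 5-4). Most missingness is therefore likely to be monotone, and monotone gaps are unaffected. This too stands, but it does not empty the pattern. A missed visit, two missing items, or a missing Question 1 or 7 loses a single ACQ-7 score (SAP 2.6.1, 2.6.3). Rescue use, systemic steroids or timing can remove a Day 2 trough (SAP 2.5.3).

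Finally, the SAS code is deferred to the table shells, so the implemented model may already include Week 12. That cannot be checked here and does not correct the written list.

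**Conclusion.** The omission is in the text and conflicts with the SAP's own choice of method and assumption. It is a low-severity point and a free improvement. Slope dilution follows wherever the earlier visit is missing and Week 12 is observed. Overstatement of the Day 30 proportions needs the further assumption that gaps track Week 12 control. The sizes rest on assumed gap rates, correlation and mechanism.

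A reader might infer more, and the documents do not support it:

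- **That the Week 12 responder result is biased.** Observed Week 12 scores are kept and analysed, and the odds ratio moves only within simulation noise.
- **That the Day 30 rate is biased whatever the cause of the gaps.** With random gaps it is not.
- **That the tipping-point analysis has the same rate bias.** Its Step 3 model analyses Week 12 with no visit term, so an imputed Day 2 value acts only as a predictor for imputing Week 12. Only the slope dilution applies, and its effect on the tipping point has not been quantified.
- **That the main analyses are touched.** The primary MMRM and the ACQ-7 MMRM do not use these imputations, and power and type I error are unchanged.

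**What to change.** In SAP 6.6, add Week 12 ACQ-7 to the Day 30 predictor list of the responder analysis. In Step 1 of the tipping-point analysis, add Week 12 trough FEV1, before any delta is subtracted, to the Day 2 list. Apply the same change where the responder analysis is repeated for ACQ-5. Check that the code in the table shells matches.

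The cost is one term per imputation model, with no new data and no change for monotone dropout. Under MAR this removes the slope dilution, and it removes the Day 30 rate bias when gaps depend on observed data. If gaps depend on the unobserved Day 30 score itself, it removes only part of the bias. Reporting how many patients per arm have the earlier visit missing and Week 12 observed would show how much the change matters.
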